## 7.6 Study drug preparation and infusion

- The pharmacist will prepare the IVIG for each infusion.
- The IVIG should be inspected visually for particulate matter and discoloration prior to administration, whenever solution and container permit. Do not use if turbid and/or discoloration is observed.
- The IVIG must not be mixed with other medicinal products or administered simultaneously with other intravenous preparation in the same infusion set. Do not mix with IVIG products from other manufacturers.
- Do not freeze. Solutions that have been frozen should not be used.
- IVIG bottle is for single use only. Octagam contains no preservative. Any bottle that has been entered should be used promptly. Partially used bottles should be discarded.
- Content of IVIG bottles may be pooled under aseptic conditions into sterile infusion bags and infused within 8 hours after pooling (within 72 hours if stored at 2-8°C [36-46°F]).
- Do not use after expiration date.
- IVIG should not be diluted.
- IVIG must be allowed to warm to room or body temperature prior to infusion if stored at 2-8°C (36-46°F).
- 0.4 g/kg body weight of Octagam 10% is transferred into an EVA infusion bag.

## 7.7 Incompatibilities

Octagam must not be mixed with other medicinal products or administered simultaneously with other intravenous preparations in the same infusion set.

## 7.8 Administration

- Octagam should be at room or body temperature during administration. Only administer intravenously.
- Any bottle that has been opened should be used promptly. Partially used bottles should be discarded.
- Octagam is not supplied with an infusion set. If an in-line filter is used the pore size should be 0.2 – 200 microns.
- Do not use a needle of larger than 16 gauge to prevent the possibility of coring. Insert needle only once, within the stopper area delineated (by the raised ring for penetration). The stopper should be penetrated perpendicular to the plane of the stopper within the ring.

## 7.9 Rate of administration

The initial infusion rate of IVIG (Octagam) will be 0.01 mL/kg/min (60 mg/kg/hr) for the first 30 minutes; if tolerated, advanced to 0.02 mL/kg/min (120 mg/kg/hr) for the second 30 minutes;

if tolerated, advanced to 0.03 mL/kg/min (180 mg/kg/hr) for the third 30 minutes and, if tolerated, advanced to 0.04 mL/kg/min (240 mg/kg/hr) for the remaining time at the discretion of the treating Investigator.

If adverse events (AEs) occur during infusion, the rate should be reduced to half the rate at which the event occurred, or the infusion interrupted until symptoms subside. The infusion may then be resumed at a rate tolerated by the patient.

The batch number(s) and number of different vial sizes used will be recorded on the drug accountability form.

### **7.1 Concomitant therapy**

Concomitant medications will be assessed at all study visits. Concomitant medications are prescribed or over-the-counter medications and should be consistent with the inclusion/exclusion criteria. Concomitant medication appropriate to the subject's condition may be prescribed during the course of the study with the exception of those listed above.

Routine vaccinations (i.e., flu vaccination) with commercially available therapeutics are permitted but must not be given within four weeks before or after the administration of the study drug.

## **8 EVALUATIONS BY VISIT**

The overall summary of study activities by visit is provided Section 1.

Screening procedures at visit 1 will take place up to 28 days prior to Visit 2 (Day 1) dosing. Screening labs and assessments will be performed during the screening period. The first dose of study drug is administered on Day 1. Visits 2 through 6 have a  $\pm 1$  day window and occur every 14 days over two months. The investigator will determine if a subject is suitable to continue following a missed infusion. Visit 7 has a  $\pm 7$  day window.

All study screening data from Visit 1 including laboratory results must be reviewed for study eligibility prior to receiving first dose of study drug. Prior to infusion, a review of concomitant medications and AEs takes place. If the subject continues to be eligible for enrollment, the subject will be infused with study medication and will remain in the infusion clinic for at least 1 hour following the infusion for safety assessments on Visit 2 (Day 1), and 15 minutes for the subsequent visits.

### **8.1 VISIT 1: Screening**

The following screening procedures will occur up to 28 days prior to Visit 2 (Day 1) infusion:

- Obtain signed and dated SHIRB approved written Informed Consent from the subject and collaborative informant prior to the initiation of any screening procedure
- Assess Inclusion/Exclusion criteria
- Obtain medical history
- Record prior medications
- NIA criteria review
- Determine Rosen Modified Hachinski Ischemic score

- Record vital signs
- Perform physical examination including height and weight
- Perform neurological examination
- Obtain standard 12-lead ECG
- Conduct MMSE and CDR assessments
- Conduct Florbetapir PET (Appendix C)
- Conduct retinal amyloid imaging (Appendix D)
- Obtain blood sample for ApoE genotyping, IgA deficiency, serum viscosity
- Obtain blood sample for complete blood count (CBC) and comprehensive metabolic panel (chemistry panel).
- Obtain blood sample for thyroid stimulating hormone (TSH), vitamin-B12 and rapid plasma reagin laboratory tests

## 8.2 VISIT 2: Day 1 – First infusion

The investigator will confirm that subjects are still eligible by reviewing all screening data. Subjects who no longer meet criteria will not be eligible for enrollment in the study.

- Confirm that subjects continue to meet inclusion/exclusion criteria
- Assess and record AEs
- Record concomitant medications
- Record vital signs
- Perform physical and neurological examinations (may occur within 72 hours prior to first infusion)
- Preparation of study drug by pharmacists and deliverer to the infusion administration site.

### 8.2.1 Study drug infusion:

- Subjects will be given the option of prophylaxis oral acetaminophen, diphenhydramine, or both 15-30 minutes prior to infusion
- Measure blood pressure, pulse rate, temperature and respiratory rate within 15 minutes prior to start of the infusion
- Administer study drug to the subject by intravenous infusion

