16. Other clinically significant abnormality on physical, neurological, laboratory, vital signs or ECG examination (e.g., atrial fibrillation) that could compromise the study or be detrimental to the subject.
17. Weight greater than 120 kg (264 lbs).
18. Excessive smoking defined as more than 20 cigarettes per day.

19. History of alcohol or drug dependence or abuse as defined by DSM-IV criteria within the last 2 years.
20. Severe liver or kidney disease verified by the PI review of ALT, AST and creatinine.
21. Known coagulopathy, thrombosis, or low platelet count.
22. Hemoglobin less than 11 g/dL.
23. Known deficiency to IgA.
24. Positive serology for Hepatitis B or C, or HIV.
25. History of anti-amyloid treatment, immunotherapy, or other experimental treatment for MCI or Alzheimer disease.
26. Concurrent use of anticholinergic drugs including diphenhydramine.
27. Current use of anticoagulant medications (except the use of aspirin 325 mg/day or less, plavix, aggrenox, and persantine but not for stroke).
28. Concurrent use of opioid pain relievers and related synthetic derivatives.

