### **6.1 Enrollment**

A subject is considered enrolled when they have completed informed consent and received any amount of IVIG by infusion.

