### **8.3 VISIT 3 (Day 14 - Second Infusion) through VISIT 6 (Day 56 - Fifth Infusion)**

- Assess and record AEs
- Record concomitant medications
- Record vital signs
- If there is any abnormality of vital signs or clinical concerns during infusion visit, the principle-investigator or sub-investigator will be paged in order to perform a clinical assessment.
- Preparation of study drug by pharmacists and deliverer to the infusion administration site.
- Administer drug as stated in 8.2.1 and 8.2.2
- Subjects will remain in the clinic for at least 15 minutes following the completion of the infusion. The subjects may leave the clinic after the observation period if the subject is medically stable.

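### Does offering diphenhydramine before each infusion, when exclusion 26 names that drug, put eligibility or the results at risk?

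*Combined protocol and SAP*

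**What the plan says.** Exclusion 26 in Section 5.2 reads "Concurrent use of anticholinergic drugs including diphenhydramine". It has no exception, whereas exclusion 27, on anticoagulants, lists the drugs it allows.

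Section 8.2.1, which describes the first infusion, states: "Subjects will be given the option of prophylaxis oral acetaminophen, diphenhydramine, or both 15-30 minutes prior to infusion". For Visits 3 to 6, Section 8.3 adds "Administer drug as stated in 8.2.1 and 8.2.2", so the offer applies to all five infusions.

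The Concomitant therapy section (numbered 7.1, following 7.9) states: "Concomitant medications are prescribed or over-the-counter medications and should be consistent with the inclusion/exclusion criteria". It goes on to allow treatment suited to the subject's condition during the study, apart from drugs listed earlier.

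Three further provisions bear on timing at Visit 2:
- Section 6.1: "A subject is considered enrolled when they have completed informed consent and received any amount of IVIG by infusion".
- Section 8: "Prior to infusion, a review of concomitant medications and AEs takes place", followed by "If the subject continues to be eligible for enrollment, the subject will be infused with study medication".
- Section 8.2: "Subjects who no longer meet criteria will not be eligible for enrollment in the study".

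**The concern.** The same drug is named in an exclusion criterion and in a planned study step, so the conflict needs no inference about drug class. At Visit 2 it also looks like an eligibility problem. Enrollment happens only when IVIG starts, so a dose taken 15 to 30 minutes earlier comes before enrollment. Read strictly, the protocol would offer a subject a drug that disqualifies that subject just before the act of enrollment.

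What might be at stake is who ends up in the sample. Section 9.1 lets the investigator withdraw a subject for a significant protocol violation, without defining one, and Section 9.2 replaces anyone who does not complete five infusions. With five subjects in an open-label study, one person is 1/5 = 20% of the data. An unwritten ruling on premedication could then seem able to decide whose results are graphed.

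**Working it through.** The protocol gives no figure to reproduce on this point. The check is a comparison of the sections, with some simple counts.

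**1. Is there a conflict?** Yes. Exclusion 26 names the drug, Sections 8.2.1 and 8.3 offer it, and neither they nor the Concomitant therapy section writes an exemption. Two readings soften this. Concurrent use is not defined and could mean ongoing use, and Section 8.2.1 could be read as a specific permission. Neither reading is spelled out.

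**2. Where is the conflict stronger?** On study, more than at entry. Section 8.2 lists the eligibility confirmation, based on screening data, and the recording of concomitant medications before the infusion steps in 8.2.1. Section 8 places the medication review before the infusion and does not ask for a second check after premedication. Section 1 schedules the inclusion/exclusion check at Visits 1 and 2 only. The Concomitant therapy section, by contrast, covers medication taken during the study, if its reference to drugs listed earlier means the exclusion list.

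**3. How many occasions?** With five subjects (Section 15) and five infusions each:
- Visit 2: 5 × 1 = 5 offers.
- Visits 3 to 6: 5 × 4 = 20 offers.
- Total: 5 + 20 = 25 offers, before any replacements.

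Acceptance is not stated, so the number of doses could be anything from 0 to 25. That is the full possible range and does not measure impact.

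**4. Does the route to the sample hold?**
- On the strict Visit 2 reading, the subject gets no IVIG and under Section 6.1 is never enrolled. That is an entry failure, so withdrawal under 9.1 and replacement under 9.2 are not the mechanism.
- If the subject is infused, any issue is an on-study deviation, and the enrollment timing adds little. Removal would require the investigator to call acceptance of a protocol-offered drug a significant violation. No section suggests this, withdrawal is discretionary, and Section 12 lets the principal investigator approve minor deviations.
- Section 9.2 replaces subjects who miss infusions. It has no provision for removing someone who completed all five.
- The scheduled follow-up imaging comes after the last infusion, so a Visit 2 eligibility decision is made before that subject's change in either marker is known.

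**5. Could the doses affect the endpoints?** Sections 3.2 and 14.1 name two measures, and Section 14.1 plans graphs of individual changes. Section 1 places baseline imaging at screening, before any offered dose, and follow-up imaging at Month 3. Counting 30 days to a month (my assumption), Month 3 is about Day 90, which is 90 − 56 = 34 days after the fifth infusion. With visit windows of ±7 and ±1 days, the gap is 34 − 8 = 26 to 34 + 8 = 42 days. Section 8.4 heads this visit Month 4, which would lengthen the gap. MMSE and CDR are scheduled only at screening, so no later cognitive score is exposed to infusion-day dosing.

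**The case for a change.** The best case for acting is that the protocol writes exceptions where it wants them, as exclusion 27 shows, and wrote none here. Section 8 makes the infusion depend on continuing eligibility, and the infusion follows the dose. Relying on Section 12 would mean treating a planned step as a deviation that needs approval. One person could classify a dose under Section 5.2 and another under Section 8.2.1, and no text says which prevails. The remedy would be one or two sentences.

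Most of that stands as a description of the wording. The sections do disagree, and deviation recording is ambiguous for any accepted dose. The step to consequences does not stand. Losing eligibility after premedication would need a re-check that no section schedules, and the withdrawal and replacement route does not follow from a strict reading at entry. The study has a single center (Section 4.1), so different sites cannot apply different rules. The remedy is also not free: Section 17.4 requires the principal investigator's agreement, review by the company supplying the drug, and IRB approval before an amendment takes effect. In return it would settle how a dose is labeled and leave the planned graphs as they are.

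**Conclusion.** This is a genuine but minor wording inconsistency, and no change to the design, sample size or analysis follows from it. Exclusion 26 and the Concomitant therapy section must be reconciled with Sections 8.2.1 and 8.3 by those responsible for the clinical rules. I take no view on which rule is right.

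The shown effect on the two endpoints is nil. The 25 offers and the 20% share per subject describe the size of the study and do not estimate harm. If Section 8.2.1 is followed as a specific permission, the same subjects are infused, imaged and graphed as planned, and the proof-of-concept reading is the same.

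The conclusion assumes that eligibility is confirmed in the order Section 8.2 lists, that accepting a protocol-offered drug is not treated as grounds for withdrawal, and that accepted doses are captured in the concomitant medication record kept at every infusion visit. If the investigator did start to exclude or withdraw subjects on this ground, the make-up of the sample would need another look.

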### 8.2.2 Following initiation of infusion:

- Measure blood pressure and pulse rate at 15, 30, 60 and every 30 minute mark for the duration of the infusion
- Measure blood pressure, pulse rate, temperature and respiratory rate immediately post infusion and prior to leaving the clinic
- Assess infusion site post infusion
- Assess and record AEs

- Subjects will remain in the clinic for at least 1 hour following the completion of the infusion. The subjects may leave the clinic after the observation period if the subject is medically stable.

### **8.3 VISIT 3 (Day 14 - Second Infusion) through VISIT 6 (Day 56 - Fifth Infusion)**

- Assess and record AEs
- Record concomitant medications
- Record vital signs
- If there is any abnormality of vital signs or clinical concerns during infusion visit, the principle-investigator or sub-investigator will be paged in order to perform a clinical assessment.
- Preparation of study drug by pharmacists and deliverer to the infusion administration site.
- Administer drug as stated in 8.2.1 and 8.2.2
- Subjects will remain in the clinic for at least 15 minutes following the completion of the infusion. The subjects may leave the clinic after the observation period if the subject is medically stable.

### **8.4 VISIT 7: Month 4 (±7 days)**

- Assess and record AEs
- Record concomitant medications
- Record vital signs
- Perform physical and neurological examinations
- Record vital signs
- Assess and record AEs
- Record concomitant medications
- Obtain blood sample for routine hematology and chemistry laboratory tests
- Conduct Florbetapir PET (Appendix C)
- Conduct retinal amyloid imaging (Appendix D)

### **8.5 Early termination from the study**

Every attempt should be made to follow each subject through the final visit 7. In the event of early withdrawal from the subject for any reason, an Early Termination Visit should be completed for criteria of withdrawal. If the subject withdraws due to an AE, every attempt should be made to follow the subject until the AE resolves or until the investigator deems that the AE is stable or determined the AE to be chronic. All SAEs will continue to be followed until the end of the study (Visit 7 or ET visit) or until the SAE has resolved or the investigator deems the event to be stable or chronic.

## 9 WITHDRAWAL AND REPLACEMENT OF SUBJECTS

### 9.1 Criteria for subject withdrawal

In accordance with the Declaration of Helsinki and other applicable regulations, a subject has the right to withdraw from the study at any time and for any reason. If a subject requests or decides to withdraw, every attempt will be made to complete an early termination visit.

The investigator has the right to withdraw subjects from the study if a subject:

- Is in significant violation of the protocol
- Experiences an intolerable AE or SAE
- Is non-compliant
- Withdrawal of consent
- Lost to follow up
- Death

### 9.2 Replacement of subjects

Subjects who do not complete all five infusions will be replaced.

## 10 ADVERSE EVENTS

### 10.1 Adverse event definition

An AE is any untoward event that occurs any time after randomization to the double blind treatment until the end of study (visit 7 or ET visit). The event need not have a causal relationship with the study drug or treatment. Adverse events include, but are not limited to clinically significant changes in clinical status, physical or neurological examinations, ECG, abnormal laboratory findings, exacerbations of underlying disease, and drug interactions, dependency, misuse and abuse. All AEs must be documented on the Adverse Event page of the CRF and in the subject's medical notes. Each AE is evaluated for duration, severity, seriousness, relatedness to study drug, and action taken. The investigator may be asked to provide follow-up information.

### 10.2 Serious adverse event (SAE) definition

A serious adverse event is one that at any dose (including overdose):

- Results in death
- Is life-threatening
- Requires inpatient hospitalization or prolongation of existing hospitalization
- Results in persistent or significant disability or incapacity
- Is a congenital anomaly/birth defect
- Is a medically important condition:

Suspected transmission of an infectious agent,

Thromboembolic events,

Cerebral hemorrhage resulting in clinical disability, or

Other reactions that should be reported in an expedited manner although they did not immediately result in one of the above seriousness criteria

### **10.3 Other relevant drug safety information**

Any safety information relating to:

- Pregnancies/breastfeeding,
- Drug abuse (persistent, sporadic or intentional excessive use of a medicinal product inconsistent with the SPC or acceptable medical practice),
- Overdose (treatment exceeding the medically recommended dose),
- Medication errors (prescribing or dispensing error),
- Interactions with other medicinal products or devices
- Associated with Octagam 10%, even if no adverse drug reaction occurred.

“Life-threatening” means that the subject was at immediate risk of death at the time of the serious adverse event; it does not refer to a serious adverse event that hypothetically might have caused death if it were more severe.

“Persistent or significant disability or incapacity” means that there is a substantial disruption of a person’s ability to carry out normal life functions.

### **10.4 Adverse event severity**

Severity of AEs will be assessed using the National Cancer Institute (NCI) Common Terminology Criteria for Adverse Events (CTCAE) Version 4.0 for toxicity and adverse event reporting. A copy of the CTCAE Version 4.0 can be downloaded from the CTEP homepage (<http://ctep.info.nih.gov>). AEs not corresponding to the CTCAE term will be assessed according to their impact on the subject’s ability to perform daily activities as follows:

- Mild (grade 1) – the AE does not interfere in a significant manner with the subject’s normal functioning level. It may be an annoyance.
- Moderate (grade 2) – the AE produces some impairment of functioning, but is not hazardous to health. It is uncomfortable or an embarrassment.
- Severe (grade 3) – the AE produces significant impairment of functioning or incapacitation and is a definite hazard to the subject’s health.
- Life threatening (grade 4) – Life threatening or disabling.
- Fatal (grade 5) Causes death of the participant.

The investigator must appraise all abnormal laboratory results for their clinical significance. If any abnormal laboratory result is considered clinically significant, the investigator must provide details about the action taken with respect to the test drug and about the patient’s outcome.

### **10.5 Adverse event reporting**

All AEs, whether observed by the investigator or reported by the patient, must be recorded, with details about the duration and intensity of each episode, the action taken with respect to the test drug, and the patient’s outcome. The investigator must evaluate each adverse experience for its relationship to the test drug and for its seriousness. The initial report must

be as complete as possible, including details of the current illness and (serious) adverse event, and an assessment of the causal relationship between the event and the investigational product(s). Information not available at the time of the initial report (e.g., an end date for the adverse event or laboratory values received after the report) must be documented on a follow-up form. A final report to document resolution of the adverse event is required.

#### **10.6 Investigator reporting to the FDA**

Adverse drug reactions that are **serious, unlisted/unexpected, and at least possibly associated to the drug**, and that have not previously been reported in the Investigators brochure, or reference safety information document should be reported promptly to the FDA in writing by each investigator/physician engaged in clinical research. A clear description of the suspected reaction should be provided along with an assessment as to whether the event is drug or disease related.

The investigator/physician shall notify the FDA by telephone or by fax of any unexpected fatal or life threatening experience associated with the use of the drug as soon as possible, but no later than 7 calendar days after the sponsors initial receipt of the information. Each phone call or fax shall be transmitted to the FDA new drug review division in the Center for Drug Evaluation and Research or the product review division in the Center for Biologics Evaluation and Research that has responsibility for review of the IND if applicable.

